### **Informed Consent**

5. Capable of giving signed informed consent as described in Section 10.1 (Appendix 1), which includes compliance with the requirements and restrictions listed in the ICF and in this protocol.

## 5.2. Exclusion Criteria

Participants are excluded from study enrollment if they meet any of the following criteria at screening:

### Medical Conditions

#### *Diabetes-Related*

6. Have Type 1 diabetes mellitus (T1DM) or T2DM, history of ketoacidosis, or hyperosmolar state/coma
7. Have at least 1 laboratory value suggestive of diabetes mellitus during screening, including 1 or more of: HbA1c  $\geq 6.5\%$  ( $\geq 48$  mmol/mol), fasting glucose  $\geq 126$  mg/dL ( $\geq 7.0$  mmol/L), or random glucose  $\geq 200$  mg/dL ( $\geq 11.1$  mmol/L)

#### *Obesity-Related*

8. Have a self-reported change in body weight  $>5$  kg within 3 months prior to screening
9. Have a prior or planned surgical treatment for obesity (excluding liposuction or abdominoplasty, if performed  $>1$  year prior to screening)
10. Have or plan to have endoscopic and/or device-based therapy for obesity or have had device removal within the last 6 months prior to screening
  - mucosal ablation
  - gastric artery embolization
  - intragastric balloon
  - duodenal-jejunal endoluminal liner

#### *Other Medical*

11. Have renal impairment measured as estimated glomerular filtration rate (eGFR)  $<30$  mL/min/1.73 m^2, calculated by Chronic Kidney Disease-Epidemiology (CKD-EPI) as determined by central laboratory during screening
12. Have a known clinically significant gastric emptying abnormality (for example, severe gastroparesis or gastric outlet obstruction) or chronically take drugs that directly affect GI motility
13. Have a history of chronic or acute pancreatitis
14. Have thyroid-stimulating hormone (TSH) outside of the range of 0.4-6.0 mIU/L at the screening visit

**Note:** Participants receiving treatment for hypothyroidism may be included, provided their thyroid hormone replacement dose has been stable for at least 3 months and their TSH at screening falls within the range indicated above.

**Note:** Participants with a history of subclinical hypothyroidism but a TSH at screening within the range indicated above, may be included if in the investigator's opinion, the patient is unlikely to require initiation of thyroid hormone replacement during the course of the study.

15. Have obesity induced by other endocrinologic disorders (for example, Cushing syndrome) or diagnosed monogenetic or syndromic forms of obesity (for example, Melanocortin 4 Receptor deficiency or Prader Willi Syndrome)
16. Have a history of significant active or unstable Major Depressive Disorder (MDD) or other severe psychiatric disorder (for example, schizophrenia, bipolar disorder, or other serious mood or anxiety disorder) within the last 2 years

**Note:** Participants with MDD or generalized anxiety disorder whose disease state is considered stable for the past 2 years and expected to remain stable throughout the course of the study, in the opinion of the investigator, may be considered for inclusion if they are not on excluded medications

17. Have a lifetime history of suicide attempt
18. Have a PHQ-9 score of 15 or more at Visit 1
19. On the C-SSRS at any time from Visit 1 to Visit 2:
  - a "yes" answer to Question 4 (Active Suicidal Ideation with Some Intent to Act, Without Specific Plan) on the "Suicidal Ideation" portion of the C-SSRS
  - or**
  - a "yes" answer to Question 5 (Active Suicidal Ideation with Specific Plan and Intent) on the "Suicidal Ideation" portion of the C-SSRS
  - or**
  - a "yes" answer to any of the suicide-related behaviors (actual attempt, interrupted attempt, aborted attempt, preparatory act or behavior) on the "Suicidal Behavior" portion of the C-SSRS
  - and**
  - the ideation or behavior occurred within the past month
20. Have uncontrolled hypertension (systolic blood pressure above or equal to 160 mmHg and/or diastolic blood pressure above or equal to 100 mmHg)
21. Have any of the following cardiovascular conditions within 3 months prior to Visit 2:
  - acute myocardial infarction
  - cerebrovascular accident (stroke)
  - unstable angina, or
  - hospitalization due to congestive heart failure (CHF)
22. Have NYHA Functional Classification Class IV CHF

23. Have acute or chronic hepatitis, signs and symptoms of any other liver disease other than nonalcoholic fatty liver disease (NAFLD), or any of the following, as determined by the central laboratory during screening:

- alanine aminotransferase (ALT) level  $>3.0X$  upper limit of normal (ULN) for the reference range
- alkaline phosphatase (ALP) level  $>1.5X$  ULN for the reference range, or
- total bilirubin (TBL) level  $>1.2X$  ULN for the reference range (except for cases of known Gilbert's Syndrome)

**Note:** Participants with NAFLD are eligible to participate in this trial if their ALT level is  $\leq 3.0X$  ULN for the reference range.

24. Have a serum calcitonin level (at Visit 1) of

- $\geq 20$  ng/L, if eGFR  $\geq 60$  mL/min/1.73 m^2
- $\geq 35$  ng/L, if eGFR  $< 60$  mL/min/1.73 m^2

25. Have a family or personal history of medullary thyroid carcinoma (MTC) or multiple endocrine neoplasia (MEN) syndrome type 2

26. Have a history of an active or untreated malignancy or are in remission from a clinically significant malignancy (other than basal or squamous cell skin cancer, in situ carcinomas of the cervix, or in situ prostate cancer) for less than 5 years

27. Have any other condition not listed in this section (for example, hypersensitivity or intolerance) that is a contraindication to GLP-1R agonists

28. Have a history of any other condition (such as known drug or alcohol abuse, diagnosed eating disorder, or other psychiatric disorder) that, in the opinion of the investigator, may preclude the participant from following and completing the protocol

29. Have history of use of marijuana or tetrahydrocannabinol (THC)-containing products within 3 months of enrollment or unwillingness to abstain from marijuana or THC-containing products use during the trial

**Note:** If a participant has used cannabidiol oil during the past 3 months but agrees to refrain from use for the duration of the study, the participant can be enrolled.

30. Have had a transplanted organ (corneal transplants [keratoplasty] are allowed) or are awaiting an organ transplant

31. Have any hematological condition that may interfere with HbA1c measurement (for example, hemolytic anemias, sickle cell disease)

### ***Prior/Concomitant Therapy***

32. Are receiving or have received within 3 months prior to screening chronic ( $>2$  weeks or 14 days) systemic glucocorticoid therapy (excluding topical, intra-ocular, intranasal, intra-articular, or inhaled preparations) or have evidence of a significant, active autoimmune abnormality (for example, lupus or rheumatoid arthritis) that has required

(within the last 3 months) or is likely to require, in the opinion of the investigator, concurrent treatment with systemic glucocorticoids (excluding topical, intra-ocular, intranasal, intra-articular, or inhaled preparations) during the course of the study

33. Have current treatment with or history of (within 3 months prior to Visit 2 ) treatment with medications that may cause significant weight gain, including but not limited to: tricyclic antidepressants, atypical antipsychotics, and mood stabilizers

**Examples:**

- imipramine
- amitriptyline
- mirtazapine
- paroxetine
- phenelzine
- chlorpromazine
- thioridazine
- clozapine
- olanzapine
- valproic acid (and its derivatives), or
- lithium

*Note:* Selective serotonin reuptake inhibitors (SSRIs) other than paroxetine are permitted.

34. Have taken, within 3 months prior to Visit 2, medications (prescribed or over-the-counter) or alternative remedies that promote weight loss

**Examples include, but are not limited to:**

- Saxenda (liraglutide 3.0 mg)
- Xenical®/Alli® (orlistat)
- Meridia® (sibutramine)
- Acutrim® (phenylpropanolamine)
- Sanorex® (mazindol)
- Apidex® (phentermine)
- BELVIQ® (lorcaserin)
- Bontril® (phendimetrazine)
- Qsymia™ (phentermine/topiramate combination)
- Contrave® (naltrexone/bupropion)

*Note:* Use of metformin, or any other glucose-lowering medication, whether prescribed for polycystic ovarian syndrome (PCOS) or diabetes prevention is not permitted.

35. Have started implantable or injectable contraceptives (such as Depo Provera®) within 18 months prior to screening

***Prior/Concurrent Clinical Study Experience***

36. Are currently enrolled in any other clinical study involving an investigational product (IP) or any other type of medical research judged not to be scientifically or medically compatible with this study
37. Within the last 30 days, have participated in a clinical study and received treatment, whether active or placebo. If the study involved an IP, 5 half-lives or 30 days, whichever is longer, should have passed
38. Have previously completed or withdrawn from this study or any other study investigating tirzepatide after receiving at least 1 dose of IP

***Other Exclusions***

39. Are investigator site personnel directly affiliated with this study and/or their immediate families. Immediate family is defined as a spouse, parent, child, or sibling, whether biological or legally adopted
40. Are Lilly employees

**5.3. Lifestyle Considerations**

Per the SoA (Section 1.3), participants will consult with a dietician, or equivalent qualified delegate, according to local standards, to receive lifestyle management counseling at Weeks -12, -11, -10, -9, -8, -6, -4 and -2 prior to randomization and then at Weeks 0, 12, 24, 36, 48, 60 and 72 post-randomization.

Diet and exercise goals established during the lifestyle consultation and the importance of adherence to the lifestyle component of the trial will be reinforced at each trial contact by study staff.

**5.3.1. Meals and Dietary Restrictions**

During the intensive lifestyle modification lead-in period, participants will receive instruction from a dietician, or equivalent qualified delegate, to reduce their daily caloric energy intake to approximately 1200 kcal/day for women or 1500 kcal/day for men for 12 weeks. During this lead-in period, up to 2 liquid meal replacements per day are permitted, but not required, to achieve the targeted energy deficit. In addition to the diet modification, participants will be encouraged to exercise on a regular basis, with a recommendation of at least 150 minutes per week of moderate intensity activity (for example, brisk walking). Participants will be counseled on behavior modification strategies to help implement and adhere to the diet and exercise recommendations. Participants who achieve a  $\geq 5.0\%$  body weight loss at the end of the 12-week lead-in period (Week 0) will proceed to randomization to either tirzepatide or placebo.

After randomization, participants will be advised to maintain their daily energy intake at 500 kcal below their individualized energy requirements (Garvey et al. 2016), as calculated by the Food and Agriculture Organization of the United Nations/World Health Organization [WHO]/United Nations University (FAO/WHO/UNU) estimates of human energy requirements, using a “sedentary” physical activity level (PAL) of 1.3 (FAO/WHO/UNU 2004).

Participants will be encouraged to maintain moderate intensity physical activity of at least 150 minutes per week. Liquid meal replacement is permitted but will not be provided during the post-randomization treatment period. The recommended macronutrient distribution will be

- maximum 30% of energy from fat
- approximately 20% of energy from protein
- approximately 50% of energy from carbohydrates, and
- an energy deficit of approximately 500 kcal/day compared to the participant's estimated total energy expenditure (TEE).

To encourage adherence, it is recommended that behavior modification tools be used, such as completion of a 3-day diet and exercise log prior to each counseling visit. During each visit, the participant's diet will be reviewed and behavior modification strategies to maximize adherence will be provided as needed.

The hypocaloric diet will be continued throughout the treatment period. If a BMI  $\leq 22$  kg/m^2 is reached, the recommended energy intake should be recalculated with no kcal deficit for the remainder of the trial.

Total energy expenditure is calculated by multiplying the estimated Basal Metabolic Rate (BMR) (see table below) with a PAL value of 1.3 (FAO/WHO/ UNU 2004), which reflects an inactive lifestyle. This calculation provides a conservative estimate of caloric requirements:

$$\text{TEE (kcal/day)} = \text{BMR} \times 1.3$$

### Equations for Estimating BMR in kcal/Day\*

Sex	Age	BMR (kcal/day)
Men	18-30 years	15.057 X actual weight in kg + 692.2
	31-60 years	11.472 X actual weight in kg + 873.1
	>60 years	11.711 X actual weight in kg + 587.7
Women	18-30 years	14.818 X actual weight in kg + 486.6
	31-60 years	8.126 X actual weight in kg + 845.6
	>60 years	9.082 X actual weight in kg + 658.5

Abbreviation: BMR = basal metabolic rate; WHO = World Health Organization.

\*Revised WHO equations (adapted from: FAO/WHO/UNU 2004).

### 5.3.2. Physical Activity

At Visit 2 and all subsequent visits, participants will be advised to increase their physical activity to moderate intensity (for example, brisk walking) for at least 150 minutes per week.

#### **5.4. Screen Failures**

Screen failures are defined as participants who consent to participate in the clinical study but are not subsequently enrolled in the study. A minimal set of screen failure information is required to ensure transparent reporting of screen failure participants to meet the Consolidated Standards of Reporting Trials (CONSORT) publishing requirements and to respond to queries from regulatory authorities. Minimal information includes demography, screen failure details, eligibility criteria, and any serious adverse event (SAE).

Individuals who do not meet the criteria for participation in this study (screen failure) may not be rescreened.

## 6. Study Intervention

Study intervention is defined as any study drug intervention, investigational intervention(s), marketed product(s), placebo, or medical device(s) intended to be administered to/used by a study participant according to the study protocol.

### 6.1. Study Intervention(s) Administered

Arm Name	Tirzepatide MTD	Placebo
Dose	10 mg or 15 mg QW	N/A
Route of Administration	SC	
Sourcing	Provided centrally by the sponsor and dispensed via IWRS	
Packaging and Labeling	Study drug intervention will be provided in autoinjectors (single-dose pens) packaged in cartons to be dispensed. Clinical study materials will be labeled according to country regulatory requirements.	

Abbreviations: IWRS = interactive web-response system; MTD = maximum tolerated dose; N/A = not applicable; QW = once-weekly; SC = subcutaneous.

There are no restrictions on the time of day each weekly dose of study drug is given, but it is advisable to administer the SC injections on the same day and same time each week. The actual date, time, and injection site location of all dose administrations will be recorded in the diary by the participant. If a dose of study drug is missed, the participant should take it as soon as possible unless it is within 72 hours of the next dose, in which case, that dose should be skipped and the next dose should be taken at the appropriate time. The day of weekly administration can be changed if necessary, as long as the last dose was administered 72 or more hours before.

All participants will inject study drug SC in the abdomen or thigh using the injection supplies provided; a caregiver may administer the injection in the participant's upper arm. The injection-site location of all dose administrations will be recorded in the diary by the participant. A new autoinjector will be used for each injection. If study drug is to always be injected in the same body region, participants should be advised to rotate injection sites each week.

#### 6.1.1. Medical Devices

The combination products provided for use in the study are tirzepatide investigational autoinjector (or matching placebo). Any AE resulting from device deficiencies, misuse, or malfunctions must be detected, documented, and reported by the investigator throughout the study (see Section 10.4.3).

## 6.2. Preparation/Handling/Storage/Accountability

- The investigator or designee must confirm appropriate storage conditions have been maintained during transit for all study drug intervention received and any discrepancies are reported and resolved before use of the study drug intervention.
- Only participants randomized in the study may receive study drug intervention. Only study personnel may supply, prepare, or administer study drug intervention. All study drug intervention must be stored in a secure, environmentally controlled, and monitored (manual or automated) area in accordance with the labeled storage conditions with access limited to the investigator and authorized study personnel.
- The investigator or authorized study personnel are responsible for study drug intervention accountability, reconciliation, and record maintenance (for example, receipt, reconciliation, and final disposition records).
- Further guidance and information for the final disposition of unused study drug interventions are provided in the study training materials.

## 6.3. Measures to Minimize Bias: Randomization and Blinding

This is a double-blind, randomized study.

Participants who meet all criteria for enrollment will undergo a 12-week intensive lifestyle modification lead-in period. Those who achieve  $\geq 5.0\%$  weight loss at Visit 10 will be randomized to one of the study treatment groups (tirzepatide MTD or placebo) for the duration of the treatment period. Assignment to treatment groups will be determined by a computer-generated random sequence using an IWRS. Participants will be randomized in a 1:1 ratio to receive tirzepatide MTD or placebo.

The randomization will be stratified by country, sex (female, male), and percent weight loss at the end of lead-in ( $<10\%$  versus  $\geq 10\%$ ).

Investigators, site staff, clinical monitors and participants will remain blinded to the treatment assignments until the study is complete.

Emergency unblinding for AEs may be performed through the IWRS. This option may be used ONLY if the participant's well-being requires knowledge of the participant's treatment assignment. All emergency unblinding events are recorded and reported by the IWRS.

If an investigator, site personnel performing assessments, or participant is unblinded, the participant must be discontinued from the study. In cases where there are ethical reasons to have the participant remain in the study the investigator must obtain specific approval from a Lilly clinical research physician (CRP) for the participant to continue in the study.

In case of an emergency, the investigator has the sole responsibility for determining if unblinding of a participant's treatment assignment is warranted for medical management of the event. The participant's safety must always be the first consideration in making such a determination. If a participant's treatment assignment is unblinded, Lilly must be notified immediately. If the investigator decides that unblinding is warranted, it is the responsibility of the investigator to promptly document the decision and rationale and notify Lilly as soon as possible.

#### **6.4. Study Intervention Compliance**

Participant compliance with study drug intervention will be assessed at each visit (after randomization). Study drug compliance will be determined by the following:

- Study drug administration data will be recorded by the participant and reviewed by the investigator at each study visit.
- The participants will be instructed to return any unused study drug and/or empty cartons at the next office visit to the study site for the purpose of performing drug accountability.

Treatment compliance for each visit interval is defined as taking at least 75% of the required doses of study drug. Similarly, a participant will be considered significantly noncompliant if he or she is judged by the investigator to have intentionally or repeatedly taken more than the prescribed amount of medication (more than 125%).

In addition to the assessment of a participant's compliance with the study drug administration, other aspects of compliance with the study treatments will be assessed at each visit based on the participant's adherence to the visit schedule, completion of study diaries, and any other parameters the investigator considers necessary.

Participants considered to be poorly compliant with their study drug and/or the study procedures will receive additional training and instruction, as required, and will be reminded of the importance of complying with the protocol.

#### **6.5. Concomitant Therapy**

Participants will be permitted to use concomitant medications that they require during the study, except certain medications (for example, other medications for weight management, see Section 5.2) that may interfere with the assessment of efficacy and safety characteristics of the study treatments.

Participants who develop diabetes during the study may initiate medication for glucose control, with the exception of dipeptidyl peptidase 4 (DPP-4) inhibitors or GLP-1R agonists. Initiation of metformin for the treatment of diabetes is permitted, but metformin should not be initiated during the study for the treatment of other metabolic conditions (for example, PCOS, diabetes prevention). Management of incident diabetes should be performed by participants' usual care providers.

Investigative site staff will inform participants that they must consult with the investigator or a designated site staff member upon being prescribed any new medications during the study. This may not be possible when initiated for treatment of medical emergencies, in which case, the participant will inform the investigator or a designated site staff member as soon as possible.

Non-study medications taken by participants who are screened but not enrolled will not be reported to Lilly unless an SAE or AE occurs that the investigator believes may have been caused by a study procedure.

## **6.6. Dose Modification**

### **6.6.1. Tirzepatide**

Tirzepatide is given QW by SC injection. There are no restrictions on the time of day each weekly dose of tirzepatide is given, but it is advisable to administer the SC injections on the same day of the week and similar time each week. If a dose of tirzepatide is missed, the participant should take it as soon as possible unless it is within 72 hours of the next dose, in which case, that dose should be skipped and the next dose should be taken at the appropriate time (see Section 6.1).

Study drug dose modification is not permitted, except for management of intolerable GI symptoms from Week 0 to Week 24 (see Section 6.6.2).

### **6.6.2. Management of Participants with Gastrointestinal Symptoms**

Participants who experience intolerable GI symptoms (for example, nausea, vomiting, or diarrhea) at any time during the study, should first be counseled on dietary behaviors that may help mitigate nausea and vomiting (for example, eating smaller meals, splitting 3 daily meals into 4 or more smaller ones, and stopping eating when they feel full) (see Section 10.9). If symptoms persist, the participant should be prescribed, at the investigator's discretion, symptomatic medication (for example, antiemetic or antidiarrheal medication). A temporary interruption of study drug for 1 dose is permitted, provided the participant has taken the last 3 weekly doses. Study treatment should be resumed immediately, either alone or in combination with symptomatic medication, which can also be utilized to manage symptoms. Management of study drug after interruptions >1 dose is discussed in Section 7.1.1.

During the first 24 weeks of the treatment period (20-week dose-escalation plus 4 weeks), if intolerable GI symptoms (for example, nausea, vomiting, or diarrhea) persist despite the above measures, the investigator should contact Lilly to consider a dose de-escalation step with subsequent re-escalation (Section 4.1.1.2.3). During the remaining treatment period (Week 24 to Week 72), dose de-escalation with subsequent re-escalation, or dose de-escalation to a lower maintenance dose, is not permitted. Those with intolerable GI symptoms that develop after 24 weeks and persist despite the above measures (for example, dietary counseling, symptomatic medication, and interruption of study drug for one dose) should discontinue study drug but remain in the study for continued follow-up.

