Lifestyle Program Instruction only			X		X		X		X																								
Thyroid stimulating hormone	X																																
Immunogenicity (includes PK sample)										X	X		X			X													X		X	X	
	In the event of systemic drug hypersensitivity reactions (immediate or nonimmediate), additional unscheduled samples should be collected as detailed in Section 8.3.2.7 (Hypersensitivity Reactions). Immunogenicity samples and PK samples for immunogenicity must be taken prior to drug administration.																																
Stored Samples																																	
Pharmacogenetic sample										X																							
Nonpharmacogenetic sample	X									X			X			X						X								X		X	X
Randomization and Dosing																																	
Randomization										X																							
Dispense study intervention(s)										X	X	X	X	X	X	X			X			X			X								
Observe participant administer study drug intervention										X																							
	Participants should administer their first dose of study drug at the end of Visit 10, after other study procedures are completed.																																
Participant returns study drug intervention and injection supplies											X	X	X	X	X	X			X			X			X				X		X		
Assess study intervention(s) compliance											X	X	X	X	X	X	X	X	X	X	X	X	X	X	X	X	X	X	X	X	X	X	

Abbreviations: CKD-EPI = Chronic Kidney Disease-Epidemiology; C-SSRS = Columbia Suicide Severity Rating Scale; Cr = creatinine; ED = early discontinuation; eGFR = estimated glomerular filtration rate; HbA1c = hemoglobin A1c; IWQOL-Lite-CT = Impact of Weight on Quality of Life-Lite-Clinical Trials Version; PGIs = Patient Global Impression of status for physical activity; PHQ-9 = Patient Health Questionnaire-9; PK = pharmacokinetics; SF-36v2 acute form = Short Form-36 Version 2 Health Survey acute form; SoA = schedule of activities; TxP = treatment period; wks = weeks.

Note:

- The visit date is determined in relation to the date of Visit 2 for the lead-in period and Visit 10 (randomization) for the treatment period.

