### ***End of Visit 10 to Visit 28***

During the treatment period, office visits will occur as indicated in the SoA (Section 1.3). Telephone visits will occur at 4-week intervals between the office visits starting at Visit 17.

Office visit procedures should be conducted according to the SoA (Section 1.3), and will include

- weight, waist circumference and vital signs measurements
- laboratory testing
- administration of PRO questionnaires
- collection of AEs, product complaints and concomitant medications
- Mental Health questionnaires
- review of participant diary information (to include reinforcement and compliance assessments for study drug administration and lifestyle goals)
- drug dispensing.

Patient-reported outcomes questionnaires should be administered as early as possible, as per Suggested Visit Structure (Section 10.8). Preferred administration order is the same as Visit 2.

Mental Health questionnaires should be completed after the assessment of AEs.

Dietician consultations occur every 12 weeks from Week 0 to Week 72. Study drug and injection supplies will be returned per the SoA (Section 1.3) and according to local requirements. New supplies will be dispensed as needed.

The starting dose of tirzepatide is 2.5 mg QW (or matching placebo) for 4 weeks, then the dose is increased by 2.5 mg (or matching placebo) every 4 weeks (2.5 to 5 to 7.5 to 10 to 12.5 to 15 mg) up to MTD (either 10 mg or 15 mg).

Interventions to optimize study drug tolerance and adherence may be employed throughout the study and include, but are not limited to, brief temporary interruptions and use of additional medications to manage GI symptoms (for example, nausea, vomiting, and diarrhea, see Section 6.6.2. for details).

During the first 24 weeks of the treatment period (20-week dose escalation plus 4 weeks), participants unable to tolerate 2.5 mg or 5 mg despite the above measures will be discontinued from the study drug but remain in the study for continued follow up. For participants unable to tolerate any dose escalation between 7.5 mg and 15 mg inclusive, despite the above measures, the investigator should contact Lilly to consider a dose de-escalation step with subsequent re-escalation in a blinded fashion to reach either the 10-mg or 15-mg dose as described below (only 1 cycle of dose de-escalation and re-escalation is permitted during the first 24 weeks of the treatment period):

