- 7.5 mg to 5 mg, then the dose is increased by 2.5 mg every 4 weeks up to MTD (either 10 mg or 15 mg)
- 10 mg to 7.5 mg, then the dose is increased by 2.5 mg every 4 weeks up to MTD (either 10 mg or 15 mg)
- 12.5 mg to 10 mg, then the dose is increased by 2.5 mg every 4 weeks up to MTD (either 10 mg or 15 mg)
- 15 mg to 12.5 mg, then the dose is increased by 2.5 mg every 4 weeks up to MTD (either 10 mg or 15 mg)

Participants who tolerate 15 mg will continue on 15 mg as their MTD dose.

Participants who tolerate 10 mg, but do not tolerate 12.5 mg or 15 mg even after one de-escalation and re-escalation attempt, will continue on 10 mg as their MTD dose.

Participants who tolerate 12.5 mg but do not tolerate 15 mg even after 1 de-escalation and re-escalation attempt, will continue on 10 mg as their MTD dose.

Participants who do not tolerate up to 10 mg even after 1 de-escalation and re-escalation attempt, will be discontinued from the study drug but remain in the study for continued follow up.

At each of the 8 scheduled treatment period telephone visits, procedures will include

- collection of AEs, product complaints, and concomitant medications
- administration of Mental Health questionnaires, and
- review of participant diary information (to include reinforcement and compliance assessments for study drug administration and lifestyle goals).

Participants should be instructed to contact the investigative site for assistance as soon as possible if they experience any difficulties administering their study medication. Participants should also be advised about the appropriate course of action in the event that study drug is not taken at the required time (late/missing doses).

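### The 10 mg fallback after a failed 15 mg attempt falls due at about Week 26 or later, when Protocol 6.6.1 and 6.6.2, read literally, bar it

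*Protocol*

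**What the plan says.** Three parts of the protocol bear on this.

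- **Section 4.1.1.2.3 (End of Visit 10 to Visit 28).** Dosing starts at 2.5 mg and rises by 2.5 mg every 4 weeks to 15 mg. For intolerance the text states that "only 1 cycle of dose de-escalation and re-escalation is permitted during the first 24 weeks of the treatment period". It lists four entry points for a cycle: 7.5, 10, 12.5 and 15 mg. The last reads "15 mg to 12.5 mg, then the dose is increased by 2.5 mg every 4 weeks". It then sets the MTD that follows a failed cycle: "Participants who tolerate 12.5 mg but do not tolerate 15 mg even after 1 de-escalation and re-escalation attempt, will continue on 10 mg". A parallel sentence, for those whose highest tolerated level is 10 mg, applies when they "do not tolerate 12.5 mg or 15 mg even after one de-escalation and re-escalation attempt, will continue on 10 mg". Neither outcome carries a date limit.
- **Section 6.6.1.** "Study drug dose modification is not permitted, except for management of intolerable GI symptoms from Week 0 to Week 24", with a reference to 6.6.2.
- **Section 6.6.2.** In the first 24 weeks the site contacts the sponsor to consider a step down under 4.1.1.2.3. For Week 24 to Week 72, "dose de-escalation with subsequent re-escalation, or dose de-escalation to a lower maintenance dose, is not permitted". Intolerable gastrointestinal symptoms that develop after 24 weeks and persist despite the listed measures lead to stopping study drug, with the participant staying in follow-up.

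**The concern.** Section 4.1.1.2.3 orders a dose change whose timing follows from its own schedule, and Sections 6.6.1 and 6.6.2 close the window for dose changes at Week 24. If the 10 mg assignment always comes after the window closes, a site cannot obey all three sections as written.

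What is at stake is the treatment of individual participants. One instruction keeps a participant on 10 mg, one of the two doses that make up the tirzepatide arm. The other denies that dose and, for symptoms that develop after Week 24, stops study drug. Sponsor contact is specified for the step down in the first 24 weeks but not in the sentence that directs stopping, so a site could stop the drug without the inconsistency being noticed.

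**Working it through.** **Inputs from the protocol.** Start at 2.5 mg; steps of 2.5 mg every 4 weeks; four cycle entry points, each stepping down 2.5 mg and then rising every 4 weeks (4.1.1.2.3). Dose-modification window of 20 + 4 = 24 weeks (6.6.2). Treatment period of 72 weeks (4.1).

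**Assumptions.** Let k be the weeks spent at the failed dose before stepping down, and f the weeks on the 15 mg attempt after the cycle before moving to 10 mg. Weekly dosing implies k ≥ 1 and f ≥ 1. An upper value of 4 (one dose step) is used for illustration; the protocol sets no such limit.

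**Reproducing the plan's figures.** The i-th dose level starts at Week 4 × (i − 1): 2.5 mg at Week 0, 5 at 4, 7.5 at 8, 10 at 12, 12.5 at 16, and 15 at 4 × 5 = Week 20. Then 20 + 4 = 24. Both stated figures are recovered.

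**When 15 mg is reached or resumed after a cycle.** For a cycle entered at dose D:

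Week of 15 mg = start(D) + k + 4 + 4 × (15 − D)/2.5

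| Cycle entered at | Step down | 15 mg reached or resumed |
|---|---|---|
| 7.5 mg | 8 + k | 8 + k + 4 + 12 = 24 + k |
| 10 mg | 12 + k | 12 + k + 4 + 8 = 24 + k |
| 12.5 mg | 16 + k | 16 + k + 4 + 4 = 24 + k |
| 15 mg | 20 + k | 20 + k + 4 + 0 = 24 + k |

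Any cycle delays 15 mg by k + 4 weeks, which is at least 5. The earliest 15 mg attempt is therefore Week 25 from every entry point.

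**When the move to 10 mg falls.** Week = 24 + k + f.

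- k = f = 1: Week 26
- k = f = 2: Week 28
- k = f = 4: Week 32
- Step down from 15 mg at Week 24 exactly: 15 mg returns at Week 28, so 10 mg comes at Week 29 or later

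**Can the dates be pulled inside the window?** Section 6.1 allows the dosing day to move if at least 72 hours have passed since the last dose. With 72-hour spacing at both failures (k = f = 3/7), 15 mg is at Week 24.4 and the fallback at Week 24.9. With weekly spacing but a Week 20 visit 3 days early, the fallback is at 20 − 3/7 + 1 + 4 + 1 = Week 25.6. Both are still after Week 24. The measures that 6.6.2 requires first (counselling, symptomatic medication, a one-dose interruption) only push the dates later.

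**Failure at 12.5 mg.** After a cycle entered at 7.5, 10 or 12.5 mg, 12.5 mg is reached or resumed at Week 20 + k and the move to 10 mg falls at Week 20 + k + f. With k = f = 1 this is Week 22, inside the window; with k = 4 and f = 1 it is Week 25, outside. So not every 10 mg fallback is caught, but every one that follows a failed 15 mg attempt after a cycle is.

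**What turns on it.** From Week 26, 72 − 26 = 46 weeks of treatment remain; from Week 32, 72 − 32 = 40.

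**The case against.** The strongest reply is that the sections can be reconciled.

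- Section 6.6.2 itself sends the cycle to 4.1.1.2.3, which is the more specific rule and sets the outcomes.
- A participant still in the cycle has no settled MTD, so 10 mg is arguably the first maintenance dose rather than a lower one.
- In 6.6.1 the Week 0 to Week 24 phrase can be attached to the symptoms instead of the modification.
- Section 6.6.1 is not absolute elsewhere: 7.1.1 restarts participants at 5 mg after three or more missed doses, with no Week 24 limit.
- The strictest reading proves too much. It would bar the return to 15 mg as well, so a cycle begun at 15 mg could never be completed.

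Much of this stands as evidence of intent. Week 24 was probably meant to limit only when a cycle may begin. But none of these readings is written down, and the last argument confirms the inconsistency: on the literal text, 4.1.1.2.3 offers a cycle that 6.6.1 does not allow to finish. Appendix 9, which 6.6.2 cites, may settle the matter; its content is not shown in our copy.

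A reader might infer that 6.6.2 orders study drug stopped for everyone who fails 15 mg after a cycle. The text does not support that. The stop sentence covers symptoms that develop after 24 weeks. Participants who cycled at 15 mg may have had symptoms earlier, and those who cycled at a lower dose also had earlier intolerance, so recurrence is arguable. It is also open whether the fallback wording in 4.1.1.2.3 covers a cycle used at a lower dose or only one taken from 15 mg.

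**Conclusion.** Wrong as written: the dosing rules contradict each other. The 10 mg assignment after a failed post-cycle 15 mg attempt falls at about Week 26 or later, and no plausible dosing interval brings it inside Weeks 0 to 24. Read literally, 6.6.1 and 6.6.2 bar both the end of the cycle and that assignment. This part rests only on the protocol's 4-week steps and at least one dose at each failed level.

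The size is less certain. If 6.6.2 were followed, an affected participant could lose up to about 46 weeks on 10 mg (about 40 if each attempt lasted 4 weeks). That depends on how the stop sentence and the fallback wording are read, and it is not a firm estimate. The documents do not give the number of participants on this path; it is likely small.

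A reader might also infer a threat to the primary analysis. The documents do not support one. The analysis-set definitions in Protocol 9.3 and SAP Section 3 are unaffected, and participants who stop drug stay in follow-up. A participant stopped under 6.6.2 would contribute less data to the Efficacy Analysis Set, but no bias or loss of power can be derived from that.

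**What to change.** Add to 6.6.1 and 6.6.2 that a cycle started by Week 24 may be completed after Week 24, including re-escalation and assignment to 10 mg as MTD under 4.1.1.2.3. State that the ban on de-escalation and the instruction to stop study drug apply only to intolerance outside such a cycle. New de-escalations after Week 24 stay barred. Confirm that IWRS and Appendix 9 follow the same rule.

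The cost is a short protocol amendment with ethics approval and, if it counts as substantial, health authority approval (10.1.1), plus the IWRS check. Neither the SAP nor 7.1.1 needs changing.

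One practical matter is not a cost of this fix. In our copy of the Schedule of Activities, no dispensing is scheduled between Week 24 and Week 36, and Visits 17 and 18 are by telephone. Dose changes at about Weeks 25 to 32 may therefore need an unscheduled supply visit, but that already follows from 4.1.1.2.3 as it stands.
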